Hypothesis and Specific Aims	
Hypothesis#1: A 12-month treatment with combination ACTHar gel and Tacrolimus therapy will be superior to ACTHar gel therapy alone in lowering urinary protein to creatinine (UP/Cr) ratios in patients with idiopathic DNA-JB9 positive Fibrillary GN
 
Specific Aim #1-will randomize 35 patients with biopsy proven DNA-JB9 positive Fibrillary glomerulopathy to receive a 12-month course of ACTHar gel at 80 units SQ 2X/week alone or in combination with oral Tacrolimus at 1.0 mg BID (targeting for trough Tacrolimus dose of 4-6 ng/ml).
 
Hypothesis#2: Treatment with combination ACTHar gel and Tacrolimus therapy will result in a higher eGFR after 24 months of follow up than patients randomized to ACTHar gel therapy alone
 
Specific Aim #2-will determine the change in eGFR from baseline to 24 months of follow for patients with biopsy proven DNA-JB9 positive Fibrillary glomerulopathy. It is anticipated that at 24 months (12 months after completing therapy) patients randomized to ACTHar gel plus Tacrolimus will have higher eGFR compared to patients receiving ACTHar gel alone.
 
Hypothesis #3: Combination therapy of ACTHar Gel and Tacrolimus in patients with DNA-JB9 positive Fibrillary Glomerulopathy will lead to significantly lower urinary markers of podocyte injury compared to patients receiving ACTHar gel therapy alone.
 
Specific Aim #3-will compare the relative changes in the following urinary biomarkers will be performed:
 
1. Urinary VEGF 121, VEGF-1652. Urinary VEGF-189, VEGF-2063. Urinary MCP-14. Urinary Synaptopodin5. Urinary TGF-beta6. Urinary Podocalyxin7. Urinary Nephryn 
Levels will be measured at baseline prior to treatment and after 12 months of ACTHar ge therapyl alone or in combination with oral Tacrolimus. The relative reduction urinary biomarkers will also be compared between the two treatment groups.

Study Population	
A total of 34 patients will be enrolled.
 
Group 1 (17 patients) ACTHar gel 80 units 2X/week alone for 12 months of therapy.
 
Group 2 (17 patients) ACTHar gel 80 units 2X/week plus oral Tacrolimus 1.0 mg BID titrated to trough Tacrolimus levels between 4-6 ng/ml
 
Anticipated drop out rate 10%.

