
Number of total Clinic Visits
 
FACT-Trial: Study Design
	
conference call with the prospective patient will be arranged to discuss in details of the study; the risks/benefits of the study drug, as well as details regarding patient requirements and travel to and from the study site. The patient will be given time to review the consent with their families and other physicians.
 
If is determined by the Medical Director and the FACT Site PI that the patient is a likely candidate for the study, a travel agent will contact patient and make arrangements for airfare and overnight accommodations to visit the FACT PI. Both the airfare and overnight accommodations will be provided by NephroNet. If a patient lives within approximately 4 hours of the FACT site, they will be reimbursed for mileage and hotel. There will be a total of 13 visits per patient per site.
 
Patients agreeing to participate in the FACT sign consent at their first screening visit.
 
Thirteen (13) visits for total study: Pre-screening visits- two (2) Study Drug Treatment visits- six (6) Post Study Drug Treatment visits- five (5)
 
Study Design: This study will be a multi-center, prospective, randomized, open-labeled intervention trial of 34 patients randomized to 52 weeks of ACTHar gel alone or ACTHar gel plus oral Tacrolimus.
 
Drug Dosing:
 
Group-1: ACTHar gel alone-patients will be receive 80 units SQ Q 2X/week for 52 weeks
 
Group-2: ACTH gel 80 units 2X per week plus oral Tacrolimus (1.0 mg BID) titrating to a trough level of 4-6 ng/ml for 52 weeks
 
Note: Patient with type II diabetes will be allowed to dose at 24 units/day (0.3 mls SQ Q day) to reduce glucose fluctuations and simplify management of diabetes at the discretion of the PI.
 
Protocol-Schedule and Follow Up: Clinic Visits:

---	--

- **Visit 1: Pre-Randomization Screening & Consenting Visit:** Patients that have gone through the Pre-screening review and considered to be eligible for study participation will be seen by the local site PI for formal consenting two months prior to study randomization. The patient will then be seen by the FACT trial site PI who will perform a complete physical exam and obtain routine laboratory testing including a urine to protein Cr ratio.

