- **Visit 4: 14 Days Post Randomization Visit:** 14 Days Post Randomization (Visit 4) will be optional for patients traveling from long distances. Would request that patient visit nephrologist in home town if any adverse events of concern are reported.
- **Visits 5 – 7: Study Visits-Months 3 (V5), 6(V6) & 9(V7) :** We will be conducted in like manner to Randomization visit. Each patient will get a complete physical exam. Standard blood and urine studies will be performed as well as plasma, serum and urine study sample collections. Tacrolimus Trough Levels will be drawn for those patients randomized to the Tacrolimus arm.
- **Visit 8: Month 12: Primary Endpoint Evaluation:** All patients completing of 52 weeks of ACTHar gel therapy alone or in combination with Tacrolimus will be examined for their change in UP/Cr as compared to their baseline levels of urinary protein. Patients will be asked to bring 2 first morning voids of urine. These two samples will be averaged and used for

determination of the percentage of patients achieving the primary endpoint.

Complete Responders: < 300 mg/gm UP/Cr ratio

Patients that have reached this milestone will be weaned off ACTHar Gel with or without Tacrolimus over the subsequent 14 days.

Sites will start the ACTHar Gel wean at 40 units and reduce over a 2 week taper period at the discretion of the principal investigator of each site.

Non-or Partial Responders: > 50% Reduction in UP/Cr ratio to minimum value of 2000 mg/gm:

Patients will follow the same weaning protocol as the complete responders described above.

- **Visit 9: ACTHar Washout Visit:**

14 Days Post End of Treatment (Visit 9) will be optional for patients traveling from long distances and will occur after the post treatment taper. The Study Staff will request that the patient visit a Nephrologist in the patient's home town if any adverse events of concern are reported.

- **Visits 10 -12: Follow-Up Visits-Months 15 (V10), 18(V11) & 9(V12):** We will be conducted in like manner to Randomization visit. Each patient will be get a complete physical exam. Standard blood and urine studies will be performed as well as plasma, serum and urine study sample collections.

- **Visit 13: Month 24 Visit: Secondary Endpoint Evaluation:**

Patients completing 104 weeks of study participation will be evaluated for the following:

1) Percentage of Complete Responder patients weaned off ACTHar gel and Tacrolimus that developed a relapse after 12 months of no therapy.

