2) Percentage of patients in the ACTHar gel alone group that demonstrated additional reduction in UP/Cr

ratio following the addition of Tacrolimus at Week 52.

Hyperkalemia: Patient developing hyperkalemia defined as > 5.5 meq/L will undergo the following interventions:

Intervention #1: Review dietary sources of potassium and assess patient compliance with prescribed dietary restrictions.

Intervention #2: Adding or increasing dose of a loop diuretic. If they patient was already taking a diuretic as part of their standard of care regimen, the dose or frequency will be increased according to the discretion of the Site PI.

Intervention #3: For patients with continued hyperkalemia following intervention 1 & 2, the Site PI can consider adding a Thiazide diuretic (HCTZ or Metolazone) to the current loop diuretic.

Intervention #4: For patients with continued hyperkalemia following intervention 1 & 2 & 3, the dose of Tacrolimus can be reduced to 0.5 mg BID.

Combining Thiazide and Loop diuretic therapy to AM-PM doses

Intervention #5: For patients with continued hyperkalemia following intervention 1 & 2, 3, & 4, the patient can discontinued from Tacrolimus.

Note: Any Site PI that chooses to treat a study patient's hyperkalemia with Patiromer may do and keep the patient in the study. Any decision to use Patiromer is solely at the discretion of the Site PI.

Hyperglycemia: Patients developing intractable hyperglycemia defined as > 400 mg/dl can have their current diabetic medications modified. For patients with continued hyperglycemia despite increases in diabetic therapy, the dose of ACTHar gel can be reduced by 50%. Patients with persistent hyperglycemia can be withdrawn from the study at the discretion of the Site PI.

Note: Any Site PI choosing to use of Insulin to treat a study patient's hyperglycemia can do and keep the patient in the

study. Any decision to use institute Insulin therapy is solely at the discretion of the Site PI.

Lower Extremity Edema: Patients developing increasing lower extremity edema can have their diuretic regimen increased by either dose or frequency. Patients continuing to have edema with maximal Loop diuretics can be treated with dual Loop and Thiazide diuretic therapy. All decisions as the management of lower extremity edema will be left to the discretion of the Site PI.

Statistical Analysis Sample Size and Power.

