The sample size was calculated to detect a 40% difference in the mean UP/Cr ratio after 12 -month of ACTHar gel therapy alone or with oral Tacrolimus. Analysis will be intention to treat for all patient receiving at least one week of drug therapy. Based on the estimated variability of 30% for the change in UP/Cr ratio (CV) a sample size of 17 patients per arm (total-34) will be needed to provide 80% power to see a difference with a P value of < 0.05. A Fisher exact test will be applied for comparisons of adverse event frequencies. All tests were two-tailed with a P value-0.05 considered significant.

References:

- 1) Laser Microdissection and Proteomic Analysis of Amyloidosis, Cryoglobulinemic GN, Fibrillary GN, and Immunotactoid Glomerulopathy Sanjeev Sethi,* Jason D. Theis,* Julie A. Vrana,* Fernando C. Fervenza,† Anjali Sethi,‡ Qi Qian,† Patrick Quint,* Nelson Leung,* Ahmet Dogan,* and Samih H. Nasr* *Clin J Am Soc Nephrol* 8: 915–921, 2013.
- 2) Fibrillary Glomerulonephritis: A Report of 66 Cases from a Single Institution *Samih H. Nasr,* Anthony M. Valeri,† Lynn D. Cornell,* Mary E. Fidler,* Sanjeev Sethi,* Nelson Leung,‡ and Fernando C. Fervenza‡ Clin J Am Soc Nephrol* 6: 775–784, 2011.
- 3) Fibrillary Glomerulonephritis and Immunotactoid Glomerulopathy Charles E. Alpers and Jolanta Kowalewska. *J Am Soc Nephrol* 19: 34–37, 2008.
- 4) Plasmapheresis leading to remission of refractory

14March2019

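### The primary analysis set is labelled intention to treat but requires at least one week of drug after open-label randomisation, so it is a modified (treated) set

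*Protocol*

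**What the plan says.** The rule on who is analysed is one sentence in the Protocol, under Statistical Analysis Sample Size and Power: "Analysis will be intention to treat for all patient receiving at least one week of drug therapy". The FACT-Trial Study Design entry describes a "prospective, randomized, open-labeled intervention trial of 34 patients randomized to 52 weeks of ACTHar gel alone or ACTHar gel plus oral Tacrolimus". The Study Population entry puts 17 patients in each group.

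Other places bear on who has a month-12 value:

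- Visit 8, the primary endpoint evaluation, says: "All patients completing of 52 weeks of ACTHar gel therapy alone or in combination with Tacrolimus will be examined for their change in UP/Cr". Two urine samples brought to that visit are averaged and used for "determination of the percentage of patients achieving the primary endpoint".
- Visit 13 is worded differently: "Patients completing 104 weeks of study participation will be evaluated for the following".
- The schedule of visits lists UP/Cr in the 12-month column, headed EOT-V8, with no condition that the patient is still on drug.
- The Hyperkalemia entry says: "For patients with continued hyperkalemia following intervention 1 & 2, 3, & 4, the patient can discontinued from Tacrolimus". The Hyperglycemia entry says: "Patients with persistent hyperglycemia can be withdrawn from the study at the discretion of the Site PI". Neither says what follow-up a patient has after stopping a drug.

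**The concern.** Intention to treat means that every randomised patient is analysed in the assigned arm, whatever treatment was taken. The protocol uses that label and, in the same sentence, sets an exposure condition that can only be met after randomisation. The two cannot both hold: an analysis that follows the label breaks the condition, and one that follows the condition breaks the label. A statistical analysis plan could choose between them, but the contradiction is in the protocol itself.

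Randomisation makes the two full arms comparable. It does not do so for the subsets that remain after a week on different, known regimens. If patients leave in week one for reasons that relate to both their arm and their likely proteinuria course, the remaining groups differ for reasons other than the added tacrolimus. With 17 per arm, a single exclusion is a visible fraction of the data. The result would also be reported under a label that the protocol's own rule does not meet.

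**Working it through.** The protocol gives no figure for this point, so there is none to reproduce. The claim rests on the text, and arithmetic only gives a sense of scale.

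**1. Compare the label with the rule.**

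| Element | Protocol text | Consequence |
|---|---|---|
| Allocation | Randomised (Study Design) | The reference set is all 34 randomised patients |
| Blinding | Open-label (Study Design) | Early stopping is decided with the arm known |
| Entry to analysis | At least one week of drug (Statistical Analysis) | Fixed after allocation, so a treated set |
| Label | Intention to treat (Statistical Analysis) | Does not match the rule beside it |

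**2. Check whether the condition is needed to have an outcome.** It is not. In the schedule, the first UP/Cr after baseline is at month 3 and the primary one is at month 12. A patient who stops on day 5 and stays in the study can still give a month-12 value, and the rule would discard it.

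**3. Weight of one exclusion.** With n = 17 per arm (Study Population), k excluded patients are k/n of the arm:

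- k = 1: 1/17 = 5.9%
- k = 2: 2/17 = 11.8%
- k = 3: 3/17 = 17.6%

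**4. Size of a possible shift.** Let D be the mean change in the excluded patients minus the mean change in those retained. The full-arm mean equals the retained mean plus (k/n) × D, so exclusion moves the arm mean by (k/n) × D in absolute size. The protocol gives neither k nor D. As an illustration only, assume D between 20 and 40 percentage points of change in UP/Cr:

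| k of 17 | D = 0 | D = 20 | D = 40 |
|---|---|---|---|
| 1 | 0 | 1.2 | 2.4 |
| 2 | 0 | 2.4 | 4.7 |
| 3 | 0 | 3.5 | 7.1 |

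The between-arm comparison moves by the difference of the two arms' shifts. Equal k and equal D in both arms cancel, and D = 0 gives nothing. D may have either sign, so the direction is open.

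**5. Can the stated dropout supply k?** No. The Study Population entry anticipates 10%, which is 0.10 × 34 = 3.4 patients. It does not say whether this means stopping drug or leaving the study, or when, so it is not an estimate of patients with less than a week of drug.

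**The case against.** The strongest reply is that the sentence states its condition openly, so nobody is misled about who is included, and that few patients may fail a one-week threshold. Both points are fair, and they keep the matter small. They do not make the label right, and they give no reason to prefer the restricted set when the full one is available.

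A reader might go further and infer from Visit 8 that the primary analysis is confined to patients who complete 52 weeks of therapy. The contrast with the Visit 13 wording, which speaks of study participation, makes this tempting. The documents do not support it. The statistical section is the only place that says who is analysed. Visit 8 is a visit description that also introduces the drug wean, so it naturally speaks of patients finishing treatment. The schedule lists month-12 UP/Cr without an on-drug condition. What remains is that off-drug attendance at Visit 8 is not spelled out.

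A reader might also infer that stopping tacrolimus for hyperkalemia removes patients from the combination arm only. Under the stated rule it does not: a patient who stops after week one has met the condition and is included. That step comes after four others, and the first scheduled metabolic panel after baseline is at month 3, so on the scheduled tests it falls well after week one. For the same reason, neither a Type I error figure for a completer set nor a power loss from tacrolimus stoppers would measure this defect or the cost of correcting it.

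Which drug counts towards the week in the combination arm is detail that an analysis plan commonly settles, and it is not counted here.

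**Conclusion.** The point holds in a narrow form. The protocol calls intention to treat a set that depends on drug exposure after open-label randomisation. That set is a modified (treated) set, and the exclusion it permits can bias the primary comparison.

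Bias requires that some randomised patients have less than a week of drug, that their outcomes would differ from the rest, and that this pattern differs between the arms. The protocol gives no information on any of these. Size and direction are therefore unknown, the effect is probably small, and it may be nil. The only firm number is that each excluded patient is 5.9% of an arm; the shifts tabulated above rest on assumed values of k and D.

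The Visit 8 wording is a secondary inconsistency, not evidence of a second analysis set.

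**What to change.** 1. Under Statistical Analysis Sample Size and Power, define the primary analysis set as all randomised patients, analysed in their assigned arm. Keep the at-least-one-week set as a sensitivity analysis.
2. As a consistency edit, reword Visit 8 so that month-12 UP/Cr is collected from all randomised patients still in the study, on or off drug, as the schedule already lists.
3. Reconcile that wording with the Hyperkalemia entry on stopping tacrolimus and the Hyperglycemia entry on withdrawal from the study, so that sites know which patients are still followed. This concerns data collection only and proposes no change to clinical management.

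The cost is protocol wording and the keeping of visits that are already scheduled. There is slight dilution from the few patients with less than a week of drug: if one combination patient gained none of the added effect, the arm's average added effect would be 16/17 = 94.1% of its full value. Any such patient without a month-12 UP/Cr has to be handled as missing data; the change does not recover that value.

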Indication	Reduction of urinary protein excretion & slowing of GFR progression
Projected Number Enrolled Patients:	34
Projected Number NephroNet Sites:	7-10
Background	
Fibrillary glomerulonephritis (FGN) is a rare primary glomerular disease that is characterized by glomerular accumulations of nonbranching, randomly arranged fibrils. The most common histologic presentation is mesangial proliferative with areas of sclerosis. It is unknown whether specific histologic patterns have a better or worse prognosis. The deposition of fibrils can be found in the mesangium, basement membranes of glomerular endothelial cells and within the sub-epithelial space. Fibrillary proteins differ from amyloid both in diameter, arrangement and lack of Congo red staining. A recent review of all renal biopsies Arkana Laboratories between 2014-2015 demonstrated that 105 patients were diagnosed with Fibrillary GN (unpublished data). The mean age of these patients was 60 years old with a mean eGFR of 45 mls/min and UP/Cr ratio of 5.380 grams. The majority of these patients had been previously treated with 2 or more different immunosuppressive agents with little to no success.
 
There are currently no approved or generally accepted therapies for Fibrillary GN. Previous studies have shown that up to 70% of patients progress to ESRD within 4years⁹. Rituximab has been studied in two previous trials with an approximate response rate of 20%. A recent study treated 15 patients with refractory Fibrillary GN for an average of 6 months with ACTHar gel and achieved a complete or partial remission 59% of patients. Among the 7 ACTHar responsive patients, the UP/Cr ratio dropped by 75% from a mean of

Background

5435 to 1335 mg/gm. The efficacy of combination therapy with ACTHar and Tacrolimus was recently shown in a study of 22 patients with idiopathic Membranous GN (9) or FSGS (13). After 6 months of ACTHar gel therapy alone, 59% of patients achieved a complete or partial remission. When oral Tacrolimus was added to existing ACTHar gel, complete and partial response rates increased significantly to over 90%.

As shown in figure-1, the addition of tacrolimus to patients exhibiting a partial response to ACTH resulted in a further reduction in UP/Cr. While the number of patients in these

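### The 80% power claim is not supported: 40% and 30% give about 96% power at 17 per arm, the 30% CV is unsourced, and the scale of the 40% is undefined

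*Protocol*

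**What the plan says.** The synopsis entry Statistical Analysis Sample Size and Power gives the target: "The sample size was calculated to detect a 40% difference in the mean UP/Cr ratio after 12 -month of ACTHar gel therapy alone or with". The second arm named in that sentence is the gel combined with tacrolimus. The variability and the sample size come next: "Based on the estimated variability of 30% for the change in UP/Cr ratio (CV) a sample size of 17 patients per arm (total-34"). The claim attached to that number is that it "will be needed to provide 80% power to see a difference with a P value of < 0.05". On testing, the entry says: "All tests were two-tailed with a P value-0.05 considered significant". The Study Population entry confirms equal arms. One is given as "Group 1 (17 patients) ACTHar gel 80 units 2X/week alone for 12 months of therapy", and the comparison arm is described as "Group 2 (17 patients) ACTHar gel 80 units 2X/week plus oral Tacrolimus 1.0 mg BID". The same entry expects 10% dropout. The primary endpoint is the change in UP/Cr after 12 months.

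The synopsis Background describes a study of 15 patients with refractory fibrillary GN, treated with ACTHar gel for about 6 months, that "achieved a complete or partial remission 59% of patients". On the size of the response it says: "Among the 7 ACTHar responsive patients, the UP/Cr ratio dropped by 75% from a mean of". The two means are 5435 mg/gm before treatment and 1335 mg/gm after. It reports no SD, no non-responder values, no overall change and no definition of remission for that study.

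**The concern.** The power claim for the primary comparison depends on two numbers, and neither can be interpreted as written. The 40% is attached to the mean ratio at 12 months, while the 30% is attached to the change and called a CV. These are different scales, and moving between them needs a control-arm mean fall that the section does not give.

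The 30% also sits badly with the Background. A CV of 30% for the change means that most patients improve by similar amounts. A study in which about half respond, and responders fall by three quarters, suggests a wide spread. The comparison is relevant because ACTHar gel alone is the control treatment.

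At stake is how a non-significant result would be read. With a true 80% power for a 40% difference, it would be moderate evidence against an effect of that size. If power is well below that, it would say much less about adding tacrolimus.

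**Working it through.** **Inputs.** From the protocol: two-sided alpha 0.05, 17 per arm, difference 40%, variability 30%, dropout 10% (17 × 0.9 = 15.3, so about 15 per arm), and a pilot with 7 responders of 15 and UP/Cr from 5435 to 1335. Assumed, because not given: the shape of the distribution, non-responder change, response defined as a fall of at least 50%, equal baselines and equal SDs in both arms. Power is from the noncentral t.

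**1. The plan's own figure.** Standardised difference d = 40/30 = 1.33.
- n per arm = 2 × (1.960 + 0.842)² / 1.33² = 8.8, so 9 by the normal approximation and 10 by the t test.
- Power at 17 per arm is 96%; at 15 it is 94%.
- On the log scale, d = 0.511/√ln(1.09) = 0.511/0.294 = 1.74. This needs 7 per arm and gives over 99% power at 17.
- For 80% power, 17 per arm corresponds to d = 0.99, an SD of about 40 points for a 40-point difference.

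The stated inputs therefore do not give 17 per arm at 80% power.

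**2. The pilot.** 7/15 = 46.7%, not 59%; 0.59 × 15 = 8.85 patients. The Background also gives 59% for the 22-patient membranous/FSGS study, where 13/22 = 59.1%. The responders' fall is (5435 − 1335)/5435 = 75.4%.

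**3. Does a 30% CV fit?** Take a normal fall with CV 30% and 47% or 59% of patients reaching a 50% fall. The mean fall is then 48.8 or 53.7 points, the responder mean 61% or 64% (pilot: 75%), and about 2% of patients fall by less than 20%.

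**4. Power for a 40% relative difference in month-12 means.** With control mean fall m, the difference is 0.4 × (100 − m) points, and d is that divided by the SD. In the two-group model, responders fall 75%, non-responders fall f%, there is no spread within groups, and SD = (75 − f) × √(p(1 − p)). The first figure in each pair is for p = 7/15, the second for p = 0.59.

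| Assumption | m | SD | CV | Power, 17 per arm |
|---|---|---|---|---|
| Normal, responder mean 75% | 47.3 / 56.4 | 32.5 / 28.2 | 69% / 50% | 45% / 42% |
| Log-normal, responder ratio 1335/5435 | – | 0.93 / 0.80 (log) | – | 35% / 44% |
| Two-group, f = 0 | 35.0 / 44.3 | 37.4 / 36.9 | 107% / 83% | 50% / 40% |
| Two-group on log scale, f = 0 | – | 0.70 / 0.69 (log) | – | 54% / 55% |
| Two-group, f = 25 | 48.3 / 54.5 | 24.9 / 24.6 | 52% / 45% | 65% / 55% |
| Two-group, f = 40 | 56.3 / 60.7 | 17.5 / 17.2 | 31% / 28% | 81% / 73% |
| Two-group, f = 45 | 59.0 / 62.7 | 15.0 / 14.8 | 25% / 24% | 87% / 82% |
| Normal, responder mean 65% | 48.4 / 53.9 | 19.5 / 16.9 | 40% / 31% | 85% / 87% |

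Adding a within-group SD of 10 points to f = 40 (for example √(17.5² + 10²) = 20.1) lowers power to 69% / 61%. At 15 per arm, the log-normal row becomes 31% / 39% and the f = 25 row 59% / 50%.

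**5. Power for 40 percentage points of change.** With SD 37.4 / 36.9 (f = 0), power is 86% / 87%. With SD 32.5 / 28.2 it is 94% / 98%. Adding 20-30 points of within-group SD to the f = 0 case brings it to 66-77%. The combination arm's mean fall would be m + 40: 75% or 84% in the f = 0 case, 87% or 96% in the normal case.

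**The case against.** The strongest reply is that 30% may mean 30 percentage points, with CV a loose label. The normal model puts the pilot SD at 28-32.5 points, which brackets 30, and power for a 40-point difference is then 94-98%. The variability is attached to the change, which is the primary endpoint, so this reading is not far-fetched. Two things count against it. The protocol words the difference as one in the mean UP/Cr ratio, and the combination arm's average patient would have to match or exceed the pilot's responders. Nor does it give 80%.

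The 80% can be approached by adding something unstated. Multiplying 30 by √2 gives an SD of 42 and about 76% power, but the text already applies the 30% to the change. A literal 30% CV with a control mean fall of 57% gives 0.4 × 43 = 17.2 against 0.3 × 57 = 17.1, so d is about 1.0 and power about 81%. That may have been intended, but no mean fall is given. With 7 of 15 responding at 75%, it requires non-responders to average (57 − 35)/(8/15) = 41%.

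The limits of the pilot also stand. It is small, ran about 6 months in refractory patients, and does not define remission. The 75% is a fall between group means. The fitted normal puts 5-6% of patients above a 100% fall. A responder mean of 65% instead of 75% brings the CV to 31% if 59% respond. Averaging repeat urine samples at baseline and month 12, and any baseline adjustment, could lower the SD.

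A reader might therefore infer that true power is 35-45%, that the trial will more likely than not miss its target effect, or that only a 55-60% reduction is detectable. The documents do not support these as findings. Each follows from one choice of scale and distribution, with pilot values that are not reported.

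**Conclusion.** The 80% power claim is not supported as written. Three points need no modelling: the 30% has no source, the scale of the 40% is undefined, and 40% with 30% gives about 96% power at 17 per arm, with 10 per arm sufficient. That 59% does not match 7 of 15 is also plain.

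That a literal 30% CV is too small is a reasonable inference, not a demonstration. For a 40% relative difference in month-12 means, power is about 35-65% under most pilot-based assumptions. It reaches about 80% or more only if non-responders averaged a fall of about 40-45% with little spread, or if the responders' true mean fall was well below 75%. For a 40-point difference it is about 86% or more unless substantial within-group spread is added, but that target implies a mean fall of about 75-96% on combination treatment. The ranges assume 17 analysed per arm and that a 6-month pilot in refractory patients is informative for month 12.

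**What to change.** Rewrite the sample-size paragraph to:
- define the 40% on one scale, preferably as a ratio between arms of month-12 to baseline UP/Cr, analysed on the log scale;
- take the SD on that scale from the patient-level pilot data, including non-responders, and cite it;
- correct the Background so that the response rate and the 7 of 15 agree;
- restate power at 17 per arm and at about 15 per arm after the stated 10% dropout, or give the difference detectable with 80% power, with a sensitivity range for the SD.

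The cost is one recalculation and a reworded paragraph. No extra patients are proposed. The downside is that the stated power may become less favourable.

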
Exclusion Criteria
	
5) Note: IF UP/Cr less than 2000 mg/gm, a formal 24-hour urine collection for total protein can be performed. The total 24-hour protein will need to >= 2000mg.
 
6) Blood pressure targeted to \leq 140/90 at the time of randomization
 
7) Patients with MGUS without history of myeloma WILL be eligible.
 
8) Patients with monoclonal staining for fibrillary fibers will be excluded
 
9) Patients with Type II non-insulin dependent diabetes WILL be eligible provided the renal biopsy does not show nodular Kimmelstiel Wilson lesions
 
Exclusion Criteria;
 
1) Patients with MGUS and history of myeloma WILL NOT be eligible
 
2) Patients with active viral production of either hepatitis B or C as evidence by historical PCR test positive for active viral shedding
 
3) HIV seropositivity
 
4) Renal biopsy data with > 50% Interstitial Fibrosis
 
5) Patient with active or a known history lymphoma
 
6) Patients with insulin Dependent diabetes mellitus will be excluded
 
Note: patients with Type II diabetes mellitus that are well controlled WITHOUT the need for insulin WILL be eligible for the study.
 
7) Patients with Type II non-insulin dependent diabetes WILL be eligible provided the renal biopsy does not show nodular Kimmelstiel Wilson lesions.
 
8) Patients receiving steroids, MMF, cyclophosphamide, Azathioprine or other immunosuppressive agent with 4 weeks of study randomization Note: Washout of these medications will be allowed at the screening visit
 
9) Patients having received Rituximab or B cell modifying biologic therapy within 6 months of randomization

----------------------------------	---

Primary Endpoint:	Primary Endpoint: The change in UP/Cr ratio in patients with biopsy proven Fibrillary GN after 12 months of treatment with treated with ACTHar gel (80 units SQ 2X/week) alone OR in combination with oral Tacrolimus (1.0 mg PO BID). The change in UP/Cr for each group will also be compared to baseline UP/Cr ratios prior to randomization

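### Does 17 patients per arm fail to follow from a 40% difference, 30% variability and 80% power?

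*Protocol*

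**What the plan says.** Under Statistical Analysis Sample Size and Power, the protocol states the target effect: "The sample size was calculated to detect a 40% difference in the mean UP/Cr ratio" after 12 months of ACTHar gel alone or with tacrolimus. It then gives the variability and the result: "estimated variability of 30% for the change in UP/Cr ratio (CV) a sample size of 17 patients per arm (total-34) will be needed" for 80% power, with two-tailed tests at 0.05. The same paragraph defines who is analysed: "Analysis will be intention to treat for all patient receiving at least one week of drug therapy".

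The Primary Endpoint section names the outcome as "The change in UP/Cr ratio in patients with biopsy proven Fibrillary GN after 12 months of treatment".

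The Study Population section says "A total of 34 patients will be enrolled", lists two groups of 17, and adds directly below them "Anticipated drop out rate 10" (per cent). The study design section describes an "intervention trial of 34 patients randomized to 52 weeks of ACTHar gel alone or ACTHar gel plus oral Tacrolimus". Specific Aim #1 alone differs: it "will randomize 35 patients with biopsy proven DNA-JB9 positive Fibrillary glomerulopathy".

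**The concern.** The paragraph prints an effect, a variability, a power, a significance level and a result, so a reader will try to reproduce it. The obvious attempt divides 40 by 30 and gets a standardised difference of 1.33, for which 17 per arm is well above what 80% power requires.

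Two features of the text add to the doubt. The effect is attached to the mean UP/Cr ratio, whereas the variability is attached to the change in UP/Cr; an effect on one quantity and a CV on another do not define a standardised difference. Also, 17 per arm is called the number needed, while the same 34 is the number enrolled and randomised, so it is unclear whether the 10% dropout has been allowed for.

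This is the protocol's only planning statement for the primary comparison. If the number really contradicted its inputs, the stated 80% power could not be relied on, and the trial might be larger or smaller than its purpose requires.

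**Working it through.** **Inputs from the protocol.** Difference 40%; variability 30%, labelled CV; power 80%; two-sided alpha 0.05; 17 per arm (all from the sample size paragraph). Dropout 10% (Study Population).

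**Assumption.** The paragraph names no test for the primary comparison. I use an equal-arm two-sample t-test.

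**Method.** For standardised difference d and n per arm, power comes from the noncentral t distribution with 2n − 2 degrees of freedom and noncentrality d × √(n/2). The required n is the smallest with power of at least 80%. Dropout inflation is n/0.9, rounded up. After 10% loss, 34 × 0.9 = 30.6, about 15 per arm.

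**Reproducing the protocol's 17.** Take a change of 1.0 in one arm and 1.4 in the other, with CV 30% in each arm. The SDs are 0.30 × 1.0 = 0.30 and 0.30 × 1.4 = 0.42.

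- d = 0.4/√((0.09 + 0.1764)/2) = 0.4/0.365 = 1.096
- Power is 79.7% at 14 per arm and 82.6% at 15, so n = 15
- 15/0.9 = 16.7, so 17 per arm

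This matches the printed figure using only the protocol's own 40%, 30%, 80%, 0.05 and 10%.

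**Other readings of the same inputs.**

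| Reading | d | n per arm | n with 10% dropout | Power at 17 | Power at 15 |
|---|---|---|---|---|---|
| Difference 40, SD 30, one scale | 0.40/0.30 = 1.333 | 10 | 12 | 96.5% | 94.1% |
| Log scale, ratio 0.6, log SD √(ln 1.09) = 0.2936 | 0.511/0.2936 = 1.740 | 7 | 8 | 99.8% | 99.6% |
| Month-12 levels 1.0 vs 0.6, CV 30% per arm (SDs 0.30, 0.18) | 0.4/√((0.09 + 0.0324)/2) = 1.617 | 8 | 9 | 99.5% | 99.0% |
| Log scale, ratio 1.4, same log SD | 0.336/0.2936 = 1.146 | 13 | 15 | 90.0% | 85.8% |
| Change 1.0 vs 1.4, CV 30% per arm | 1.096 | 15 | 17 | 87.2% | 82.6% |
| Difference 40, SD of change √2 × 30 = 42.4 | 0.40/0.424 = 0.943 | 19 | 22 | 76.0% | 70.3% |

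The requirement before dropout runs from 7 to 19 per arm. The column for 17 applies if every randomised patient contributes a month-12 value; the column for 15 applies if dropouts contribute none.

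**What 17 would mean without inflation.** It is the t-test answer when the difference equals the SD (d = 1.0): power is 80.7% at 17 and 75.3% at 15. For a difference of 40 that implies an SD of about 40, not the printed 30.

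**34 against 35.** Thirty-four appears as the projected enrolment, in Study Population, in the study design section and in the sample size paragraph, and it equals 2 × 17. Thirty-five appears once, in Specific Aim #1, and cannot be two equal arms.

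**The case for a change.** The strongest case for a change is that a number recoverable by reverse engineering has still not been stated. The reading that reaches 17 needs three choices the paragraph does not make: the effect is a ratio of changes, the CV is the same in both arms, and 15 has been inflated to 17. The text puts the 40% on the mean ratio rather than on the change, and it presents 17 as the number that gives 80% power. As printed, a reader cannot tell 96.5% power from 82.6%. Nor can this be left to a SAP, since the justification of the sample size belongs in the protocol.

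Most of this stands as description: the scale and the dropout basis are unstated, and the sentence mixes two quantities. It does not establish that 17 or 80% is wrong. The reading that gives 10 per arm has to set aside the CV label and treat the 30% as an SD in percentage points. The reading that gives 17 keeps that label, keeps the CV on the change in UP/Cr, which is the primary endpoint, fits the hypothesis that the combination is superior, and uses the dropout rate printed beside the two groups of 17. Neither reading is proven, but the documents do not favour the one that produces the discrepancy.

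The omission also does not show that 17 is enough. Taking the SD of the change as √2 × 30% would need 19 per arm, or 22 with dropout. That variant fits the text less well, because the 30% is already given for the change, but it cannot be excluded.

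**Conclusion.** No change to the plan follows. The printed inputs do not determine a single sample size, but a reading that respects the protocol's own labels gives exactly 17 per arm after 10% dropout, with 82.6% power at 15 evaluable. An error in the 17 or the 80% is therefore not shown, and neither is a shortfall in power. What remains is missing detail about how the number was derived. Supplying it would mean filling in the scale, the test and the dropout basis around the same 34 patients. It would not alter the enrolment target, the primary endpoint or the analysis, because a planning assumption plays no part in the primary test once the data are in. The 35 in Specific Aim #1 is a clerical slip that the rest of the protocol resolves to 34.

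This rests on an equal-arm two-sample t-test at two-sided 0.05 and on dropouts giving no month-12 value. It gives no assurance that 17 per arm is sufficient: that depends on the true variability of the change, which the protocol gives only as an estimate without a stated scale.
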